1. The donor tissue does not provoke a rejection response in the host or cause an infection. A rejection response will be identified by leaking at the site of the graft with staining on the fluorescein and presence of inflammation in the area of the graft. The presence of inflammation is defined as seeing white edematous retina with fluid over the area of the transplant. This clinical picture would coincide with the hyperfluorescent areas seen as leakage on fluorescein. Scar tissue formation in the parenchyma of the transplant is defined as seeing fibrotic tissue in the retinal pigment epithelium and neurosensory retina in the area of the transplant.

Chronic rejection will be recognized in the clinical examination by scar tissue formation in the parenchyma of the transplant.

2. To determine that the implantation procedure will not have an adverse effect on the host eye. This is obtained by assessing the health of the retina by clinical examination, fluorescein angiography, and to rule out sympathetic ophthalmia in the fellow eye. Immediately prior to implantation, samples of the fluid surrounding the donor tissue will be taken and tested later for sterility, mycoplasma, and endotoxins.

IX. METHODS USED TO IDENTIFY, RECRUIT, AND SELECT SUBJECTS:

Sample size will be ten patients per year with Age Related Macular Degeneration (ARMD). Recruitment of subjects to undergo transplantation will be from the clinical vitreoretinal practice of [name]. Randomization is not an issue in this study as only patients who meet the criteria for macular degeneration loss of vision will be used.

Criteria for selection of patients:

Inclusion Criteria:

- The subject must have decreased central visual acuity of 20/200 or worse in one eye by ETDRS vision testing for a duration of at least one year in the operated eye and have the diagnosis of age related macular degeneration; vision in the nonoperated eye must be better than the operated eye. Vision in the operated eye cannot be better than 20/200.
- Subject is older than 55 years of age
- Patient is willing to return for follow-up visits
- Patient has signed informed consent for retinal transplantation
- Patient has undergone microperimetry and Goldmann visual field testing.

Exclusion Criteria:

- Patient having a central visual acuity of better than 20/200 in one eye by ETDRS or vision worse than 20/200 in one eye by ETDRS for a duration of less than one year
- Unwilling to sign an informed consent

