- Patient under 55 years of age
- Patient having medical problems that are contraindicatory for short-term anesthesia

- Patient unwilling to return for follow-up visits
- The patient has been determined to be pregnant by patient history or by pregnancy testing in women of childbearing potential
- Features of any condition other than age-related macular degeneration in the study eye (such as pathologic myopia or presumed ocular histoplasmosis) associated with choroidal neovascularization
- Any significant ocular disease (other than choroidal neovascularization) that has compromised or could compromise vision in the study eye and confound analysis of the primary outcome.
- Inability to obtain photographs to document choroidal neovascularization, including difficulty with venous access
- History of choroidal neovascularization in the study eye
- Participating in another ophthalmic clinical trial or use of any other investigational new drugs within 12 weeks before the start of study treatment
- Prior photodynamic therapy or Macugen therapy for choroidal neovascularization
- Patient who has a history of uveitis, Coat's disease, diabetic retinopathy, glaucoma, or a cataract that prevents visualization of the posterior pole

X. POTENTIAL RISKS:

This research procedure might have unwanted side effects for different reasons.

The known and potential risks for this trial involve standard anesthesia hazards, general and/or local. The surgery would occur under retrobulbar and/or general anesthesia. Surgical complications could result in blindness and/or loss of the eye.

Adverse effects related to the "experimental pilot trial" surgery are: (1) retinal detachment, (2) vitreous hemorrhage, (3) subretinal hemorrhage and/or subretinal proliferative tissue, (4) endophthalmitis, (5) neovascular glaucoma, (6) corneal epithelial defects, (7) cataracts, (8) diplopia, (9) ptosis, (10) prephthisis or phthisis, or (11) possible complications from anesthesia, allergic reaction or side effects from certain medicines.

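### Rejection is defined by appearance alone, so new neovascularization or surgical proliferation at the graft can be scored as rejection, and true rejection can be put down to them

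*Protocol*

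**What the plan says.** Section VIII of the protocol (criteria for success, item 1) gives two routes to a rejection.

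- **Acute:** "A rejection response will be identified by leaking at the site of the graft with staining on the fluorescein and presence of inflammation in the" graft area. Inflammation is then defined by what the examiner sees: "The presence of inflammation is defined as seeing white edematous retina with fluid over the area of the transplant". The protocol links the two signs: "This clinical picture would coincide with the hyperfluorescent areas seen as leakage on fluorescein".
- **Chronic:** "Chronic rejection will be recognized in the clinical examination by scar tissue formation in the parenchyma of the transplant". Scar is in turn defined as "seeing fibrotic tissue in the retinal pigment epithelium and neurosensory retina in the area of the transplant".

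Choroidal neovascularization appears among the exclusion criteria in Section IX, notably "History of choroidal neovascularization in the study eye" and "Inability to obtain photographs to document choroidal neovascularization, including difficulty with venous access".

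Section X lists eleven adverse effects of the surgery. New choroidal neovascularization is not named among them, but "3) subretinal hemorrhage and/or subretinal proliferative tissue" is.

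Section VII, hypothesis 2, is worded absolutely: the graft is expected to provoke no rejection. Section VIII plans ten patients, six postoperative visits over about a year, and fundus photographs with fluorescein angiography before surgery and at every visit.

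**The concern.** Neither definition asks for evidence that an immune process produced the signs. A lesion with another cause can therefore satisfy them if it sits at the graft. Two candidates matter here.

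The first is neovascularization that starts after surgery. All patients have age-related macular degeneration, all have tissue placed under the retina, and follow-up lasts about a year. It is general clinical knowledge, not something the available protocol text states, that such lesions leak on angiography, cause fluid and end in scar.

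The second is visible from the protocol alone. Section X treats subretinal proliferative tissue as a complication of surgery, while Section VIII treats fibrosis at the transplant as chronic rejection. No rule says which heading a given lesion belongs under.

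The error can run either way. Disease progression or a surgical complication may be counted against hypothesis 2 with no immune response present. Equally, a real rejection may be explained as neovascularization or surgical scar once the result is known. With ten patients and an absolute hypothesis, one eye changes the answer.

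**Working it through.** **Step 1. What each definition requires.**

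| Route | Signs required | Requirement that excludes other causes |
|---|---|---|
| Acute rejection | Leakage with staining at the graft, and white swollen retina with fluid over it | None stated; the second sign is expected to coincide with the first, so it adds little independent confirmation |
| Chronic rejection | Fibrosis in the pigment epithelium and neurosensory retina at the transplant | None stated; one sign is enough |

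The gap is widest for chronic rejection.

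**Step 2. Where other causes are handled.** Section IX removes eyes with past neovascularization. The text available has no provision for neovascularization that begins after surgery: not in criterion 1, not by name in criterion 2 (adverse effect on the host eye), and not in the Section X list. Section III mentions testing recipient blood for antibodies to MHC antigens in describing the group's clinical trials, but neither rejection definition uses that result. Part of the background, between the account of fetal tissue transplanted to the eye and the description of dry macular degeneration, was not available for this check.

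**Step 3. Size, for illustration.** The protocol gives no rejection rate, neovascularization rate or derivation of the ten patients, so there is no planned figure to reproduce. Let

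- n = 10 (Section VIII; Section IX says ten per year, and more patients would raise the chances below);
- r = probability that an operated eye develops new neovascularization during follow-up (assumed);
- s = share of those lesions that lie at the graft and meet the rejection signs (assumed).

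With q = r × s and independent eyes, P(at least one misattributed eye) = 1 − (1 − q)^10.

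- r = 5%, s = 0.5: q = 0.025, and 1 − 0.975^10 = 22.4%.
- r = 10%, s = 0.5: q = 0.05, and 1 − 0.95^10 = 40.1%.

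| r | s = 0.25 | s = 0.5 | s = 1 |
|---|---|---|---|
| 5% | 11.8% | 22.4% | 40.1% |
| 10% | 22.4% | 40.1% | 65.1% |
| 20% | 40.1% | 65.1% | 89.3% |

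These figures cover neovascularization only; surgical proliferation would add to them.

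**Step 4. Effect of one eye on the result** (exact Clopper-Pearson, two-sided 95%).

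- 0/10: upper limit 1 − 0.025^(1/10) = 30.8%.
- 1/10: lower limit 1 − 0.975^(1/10) = 0.3%; upper limit, the 97.5th percentile of Beta(2, 9), = 44.5%.

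**The case against.** The strongest reply has five parts.

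1. **The acute definition is conjunctive.** Leakage with staining, white swollen retina and fluid must all be present at the graft. Neovascularization elsewhere, or without that appearance, does not qualify. This stands. A reader might infer that conversion to wet disease *is* scored as rejection; the protocol does not say so, and only *can be* is supported. It does not help with chronic rejection, where one sign suffices.

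2. **The rates are assumed, and a new lesion is not the same as a misscored one.** This also stands. The s = 1 column assumes that every new lesion meets the definition, which the text does not support. Setting the one-sided bound for 0/10 (25.9%) beside the two-sided interval for 1/10 would exaggerate the shift; like for like, the upper limits are 30.8% and 44.5%. The protocol sets no rejection-rate threshold, so no planned boundary is crossed.

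3. **The material for telling the causes apart is already collected.** Angiograms and photographs are taken at baseline and each visit, criterion 2 covers the health of the retina, and Section X item (3) might be read to include neovascular tissue. True, but no rule says how the images decide the matter. If item (3) does cover such tissue, the same lesion can be both a surgical adverse effect and a rejection sign.

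4. **Both criteria are success criteria, and counting doubtful leaks as rejection is cautious.** Moving a lesion from one criterion to the other may leave overall success unchanged. Hypotheses 1 and 2 are nevertheless separate claims, and the protocol does not fix the cautious direction: without a rule, doubtful eyes can also be explained away.

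5. **Reading rules may sit in an analysis plan or reading manual.** They may. The criterion is nevertheless fixed in the protocol, and followed literally it can misclassify.

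**Conclusion.** The point holds in a limited form. Criterion 1 fixes rejection by appearance, and chronic rejection by a single sign of any cause. New neovascularization at the graft, or the surgical proliferation that Section X itself lists, can therefore be counted as rejection, and true rejection can be attributed to them after the fact. The direction of error is not determined.

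On the assumption that 5% or 10% of eyes develop neovascularization and half of those meet the definition, the chance of at least one misattributed eye in ten is about 22% or 40%. One such eye takes the estimate from 0% to 10%. These sizes rest on assumed rates, independence between eyes, and the clinical premise that neovascularization produces these signs. The conflict between Section X's proliferative tissue and Section VIII's chronic rejection needs none of these.

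A reader might also infer that all new neovascularization belongs under criterion 2. The documents do not support that either: criterion 2 concerns harm from the implantation procedure, and natural progression of the disease would then be booked as procedural harm.

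The change should be made, because it affects the answer to hypothesis 2 and costs little.

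**What to change.** - **Criterion 1:** for each eye that meets the rejection signs, record whether that visit's photographs and angiogram, compared with the preoperative ones, show neovascularization or surgical subretinal proliferation as the source. Class the eye as rejection, other source, both, or indeterminate. Record the class when the images are read, not after the overall result is known.
- **New neovascularization:** record it as a safety outcome of its own, without presuming that the procedure caused it, and add it to the Section X list.
- **Reporting:** give the rejection count by the definition as written (all eyes meeting the signs), and again without the other-source and indeterminate eyes. Eyes classed as both stay in each count.

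The cost is protocol wording and one extra field when reading images that are already scheduled. It requires no new visit or test and no change in treatment. The drawback is that some eyes will be indeterminate; the two counts show how far the conclusion depends on them.

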PROTOCOL

SAFETY STUDY IN RETINAL TRANSPLANTATION FOR DRY AGE RELATED MACULAR DEGENERATION

PRINCIPAL INVESTIGATOR: [name]., Clinical Professor,
Dept. Ophthalmology & Visual Sciences,
Univ. of Louisville School of Medicine;
Retina Vitreous Resource Center
Norton Audubon Hospital, Louisville

PROTOCOL NO.: WIRB[®] Protocol #20050380

CO-INVESTIGATORS: [name]., Assistant Professor;
Depts. Ophthalmology and Cell & Neurobiology,
Doheny Retina Institute
Univ. of Southern California, Los Angeles

[name]., Adjunct Professor
Dept. Anatomical Sciences & Neurobiology
University of Louisville School of Medicine

[name]., Professor;
Dept. Ophthalmology & Visual Sciences,
Dept. Psychological and Brain Sciences
Univ. of Louisville School of Medicine

[name], Transplant Immunologist,
Director Tissue Typing Laboratory,
Jewish Hospital

I. PURPOSE:

The aim of this clinical trial is to test the safety of transplanting human fetal neural retinal tissue and retinal pigment epithelium into the eyes of human patients with age-related macular degeneration. Vision in the eye to be operated on will be the poorer vision of both eyes and must be 20/200 or worse. "Retinal tissue", the layers in the back of the eye, consists of neural retina and retinal pigment epithelium. "Neural retina" is the nerve cell layer that processes light into vision. The "photoreceptor cells" in the neural retina detect the light and transform it into electrical signals, which are then transferred to the brain by other retinal cells. "Retinal pigment epithelium" (RPE) is the layer behind the neural retina which helps both to nourish the cells of

the neural retina and also to get rid of waste products. The fetal tissues used in this study will be derived from dead fetuses in the first 9-16 weeks of pregnancy obtained from elective abortions (see XV. FETAL DONOR TISSUE).

Fetal retinal transplantation is highly experimental. The research will be conducted in accordance with the prohibitions regarding the use of human fetal tissue described in Public Law 103-43, section 498B. There will be no compensation for the donor. The research will be conducted in accordance with any applicable Federal, State and local laws.

First, the technical application of the implantation instrument and its safety in the transplantation will be demonstrated in patients with 20/200 vision in one eye or worse, with functional acuity in the contra lateral eye.

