Our approach will focus on dry age-related macular degeneration. Replacement of degenerating cells by retinal pigment epithelium together with neural retina may offer success in restoring the atrophying neural retina, the pigment epithelium and part of the choroid.

VII. HYPOTHESIS TO BE TESTED:

1. Retinal transplantation by co-grafting sheets of human fetal neural retina with RPE is a safe procedure and will not have any adverse effect on the host eyes when transplanted into the subretinal space.

2. The intact sheet of transplanted human fetal neural retina with its RPE will not provoke a rejection response in the host.

VIII. DESIGN OF THE STUDY:

The participating surgeon will be [name]. The participating persons obtaining fetal retinal and RPE tissues will be [name] and [name]. [name] and [name] will participate as consultants during this project for immunology and electrophysiology testing respectively.

Before surgery, the recipient has to sign a statement that he/she is aware about the source of the donor tissue (see Research Subject Information and Consent Form), and a consent form (see Research Subject Information and Consent Form) in which the study is explained.

Ten patients with ARMD and a vision of 20/200 or worse in one eye will be selected for the study and will undergo an operation to implant fetal neural retina with RPE under the retina. Two complete examinations will be performed at least 30 days apart to confirm the visual acuity, and only one eye will be subject to surgery.

The donor tissue is taken up in a custom-made instrument with a flat, curved nozzle so that the tissue will be maintained in the correct orientation and polarity in the subretinal space of the patient's eye. (U.S. patents # 5,941,250: "Retinal tissue implantation method"; # 6,159,218: "Retinal tissue implantation tool"; # 6,156,042: "Retinal tissue implantation instrument")

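### The first exclusion criterion does not say which eye it means and does not mirror the first inclusion criterion, so read literally it bars patients whose fellow eye is better than 20/200

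*Protocol*

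**What the plan says.** Protocol section I (Purpose) describes the operated eye: "Vision in the eye to be operated on will be the poorer vision of both eyes and must be 20/200 or worse". It then says the first step will be done in patients "with functional acuity in the contra lateral eye". No acuity value is attached to that phrase.

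Section VIII (Design of the Study) is shorter: "Ten patients with ARMD and a vision of 20/200 or worse in one eye will be selected for the study".

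In section IX, the first inclusion criterion asks for ETDRS acuity of 20/200 or worse, for at least one year, in the operated eye. It adds "vision in the nonoperated eye must be better than the operated eye" and repeats the limit: "Vision in the operated eye cannot be better than 20/200".

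The first exclusion criterion in the same section starts "Patient having a central visual acuity of better than 20/200 in one eye by ETDRS or vision worse than 20/200 in one eye" and finishes "in one eye by ETDRS for a duration of less than one year". It has two limbs, better than 20/200 and recently worse than 20/200, and neither is tied to the operated eye. Three later exclusions do name the eye, for example "History of choroidal neovascularization in the study eye".

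**The concern.** An exclusion criterion is applied patient by patient and normally overrides inclusion. A patient with a poor operated eye and a good fellow eye has acuity better than 20/200 in one of the two eyes, so the first limb catches the kind of patient that section I describes. The second limb uses a different threshold from the inclusion criterion, so the two lists can disagree about the same study eye. It can also be triggered by the fellow eye.

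If staff follow the text, the trial draws from patients with poor sight in both eyes. If they follow the evident intent, each enrolled patient with a fellow eye better than 20/200 meets a written exclusion and is an eligibility deviation on paper. Neither is a good position for a ten-patient safety study.

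**Working it through.** There is no sample-size or power figure to reproduce. The check applies the criteria to example patients, reading *in one eye* as *in at least one of the two eyes* and letting an exclusion override inclusion. The acuities are illustrative; the rules come from section IX.

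**Rules as written**
- Inclusion 1: operated eye at 20/200 or worse for at least one year, and fellow eye better than operated eye.
- Exclusion 1, first limb: an eye better than 20/200.
- Exclusion 1, second limb: an eye worse than 20/200 for less than one year.

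**Example patients**

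| Case | Operated eye | Fellow eye | Inclusion 1 | Exclusion 1, literal | Study eye named, threshold unchanged | Study eye named, threshold matched |
|---|---|---|---|---|---|---|
| A | 20/400, over one year | 20/40 | met | excluded, first limb, by fellow eye | passes | passes |
| B | 20/800, over one year | 20/400, over one year | met | passes | passes | passes |
| C | 20/400, over one year | 20/250, under one year | met | excluded, second limb, by fellow eye | passes | passes |
| D | 20/200 for two years, then 20/250 for the last six months | 20/40 | met | excluded by both limbs | still excluded, second limb | passes |

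**What remains under the literal reading**
1. The first limb requires that neither eye be better than 20/200.
2. Inclusion 1 requires the fellow eye to be better than the operated eye.
3. With the fellow eye at 20/200 at best, the operated eye must then be worse than 20/200. An operated eye at exactly 20/200, which inclusion 1 accepts, could never enrol.
4. The second limb requires any eye worse than 20/200 to have been so for at least a year.

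The eligible set is therefore not empty, as case B shows. It does consist only of patients with both eyes at 20/200 or worse.

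**Could the one-year qualifier govern both limbs?** On that reading, a fellow eye that has long been good would not trigger the first limb, and case A would pass. But the first limb would then also fail to exclude a study eye that has long been better than 20/200, so it would no longer do its evident job (inclusion 1 would still bar that eye). Case D would still meet both lists.

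**What each correction does.** Naming the study eye resolves A and C and leaves B unchanged. Case D needs the threshold changed as well. With both corrections, a study eye better than 20/200, or one at 20/200 or worse for less than a year, is still excluded, which is what inclusion 1 implies.

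**The case against.** The best defence is that nobody would apply the sentence literally. The protocol uses *one eye* as shorthand for the operated eye in section VIII and at the start of inclusion 1. Exclusion 1 follows the inclusion list closely and is visibly meant as its negative, with the same test, the same 20/200 figure and the same one-year period. Inclusion 1 states the limit for the operated eye outright. Recruitment is from one clinical practice, so a misreading across many sites is not at issue. Case D is a narrow boundary case.

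Most of this stands. The intent of the first limb can be recovered, and nothing in the protocol suggests that the investigators meant to recruit patients with poor sight in both eyes. It does not dispose of the point. The text remains an operative rule that contradicts sections I and IX, and intent alone does not settle the mismatch in case D.

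A reader might go further in four ways that the document does not support:
- *The whole target population is excluded.* This holds only if functional acuity means better than 20/200, and the protocol gives no figure.
- *If the exclusion is read loosely, the ten patients are no longer a defined group.* Inclusion 1 still fixes the operated-eye limit, its duration, the diagnosis and the ordering of the two eyes.
- *A 20/400 fellow eye against a 20/800 operated eye breaks the Purpose.* Section I also describes the operated eye simply as the poorer one, which such a patient satisfies, and 20/400 is nowhere called non-functional.
- *The wording exposes patients to material added risk from sympathetic ophthalmia.* That requires literal enrolment. The rate of about 1/800 in section X, given for repeated vitreoretinal surgery, would mean 10 × 1/800 = 0.0125 expected cases in ten patients.

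**Conclusion.** The point holds as a wording error in an eligibility rule. The underlying design is not shown to be wrong. Followed as written, exclusion 1 removes every patient whose fellow eye is better than 20/200 and contradicts the population described in section I. Its second limb also conflicts with inclusion 1 for a study eye that recently fell below 20/200, and it lets a recent fall in the fellow eye exclude.

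This rests on two assumptions: that exclusions override inclusions, and that the one-year qualifier attaches to the second limb only, which is the natural grammar. Under the alternative attachment the first limb is defective in a different way and the second-limb conflict remains.

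The number of patients affected cannot be given, because the protocol states neither a fellow-eye acuity nor the distribution of fellow-eye vision in the recruiting practice. A separate, smaller looseness is that section I speaks of functional acuity in the other eye, while section IX requires only that it be better than the operated eye.

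**What to change.** Amend exclusion 1 so that both limbs name the study (operated) eye and together form the exact complement of inclusion 1: ETDRS acuity better than 20/200 in the study eye, or acuity of 20/200 or worse in the study eye for less than one year.

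The sponsor should also reconcile the fellow-eye wording of section I with that of section IX, so that both describe the same requirement. No particular acuity limit is proposed here; that is a clinical decision for the sponsor.

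The cost is a few sentences in a protocol amendment. Rewording exclusion 1 adds no patients, visits or tests, and it does not narrow the population that inclusion 1 already defines.
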